## **SAfety and Effectiveness of the Treatment of Wide Neck, Saccular Intracranial Aneurysms with the Neuroform Atlas™ Stent System**

### **Short Study Name: ATLAS**

subsequently received approval via Premarket Approval (PMA) application for use with embolic coils in the treatment of wide-neck saccular intracranial aneurysms in the anterior circulation (P180031; May 2019).

Since the original approval, stent assisted coiling using the Neuroform Stent System has been the subject of numerous scientific articles. In a meta-analysis of the published literature on the Neuroform Stent System, King et al reported that complete occlusion rates on final follow-up averaged 61.1% overall in 2,111 aneurysms treated during a 10 year period (2004 to 2014). In the treatment of wide neck aneurysms, this represents a substantial improvement in outcomes compared to embolic coiling alone.

Since the Neuroform Microdelivery System market introduction in the US, there have been a number of SAC devices approved by FDA via HDE such as the Codman Enterprise Vascular Reconstruction Device, MicroVention's LVIS device, Pulsar Vascular's PulseRider Aneurysm Neck Reconstruction Device, and Stryker Neurovascular's Neuroform Atlas Stent System. In May 2018, MicroVention's LVIS and LVIS Jr. coil assist stents received PMA approval (P170013). In May 2019, Stryker Neurovascular's Neuroform Atlas Stent System received PMA approval for use in the anterior circulation.

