### **2.4.1 Primary Endpoints**

#### **2.4.1.1 Primary Effectiveness Endpoint**

The primary effectiveness endpoint of the study is:

Complete aneurysm occlusion (100% occlusion – Raymond Class 1) of the treated target lesion on 12 month angiography, in the absence of retreatment, or parent artery stenosis (>50%) at the target location.

The Raymond Class 1 designation of complete occlusion (**Figure 1**) will be used to define occlusion success.

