### **4.2 Sample Size Estimate and Justification**

#### Anterior Circulation Cohort:

A sample size of up to 180 subjects with intracranial aneurysms in the distal anterior circulation has been selected for this study in order to provide 153 evaluable subjects at 12 months, with an estimated 15% attrition rate. Assuming an effectiveness primary endpoint response rate of 62% (per the findings of a meta-analysis of Neuroform stent literature as performed by King et al), the expected lower bound of the exact binomial two-sided 95% confidence interval around the success rate is greater than 50%. Assuming a safety primary endpoint rate of 8%, the expected upper bound of the exact binomial two-sided 95% confidence interval around the success rate is less than 20%. A sample size of 153 evaluable subjects provides 85% power to demonstrate the effectiveness endpoint, and a power of approximately 99% to successfully demonstrate the safety endpoint given the observed rates stated above. The combined probability of the two endpoints is  $(.85) \times (.99) = .842$ .

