#### Posterior Circulation Cohort:

Separate analyses of these cohort data will be performed to support an indication for use in the posterior circulation.

A sample size of up to 180 subjects with intracranial aneurysms in the posterior circulation (including vertebral, basilar and posterior cerebral arteries) will also be enrolled in order to provide 153 evaluable subjects at 12 months, with an estimated 15% attrition rate. While the safety endpoint rate for posterior circulation subjects may be higher than that for the anterior circulation subjects, that rate is not expected to exceed 12%. Assuming a safety primary endpoint rate of 12%, the expected upper bound of the exact binomial two-sided 95% confidence interval around the success rate is less than 25%. A sample size of 153 evaluable subjects provides a power of approximately 99% to successfully demonstrate the safety endpoint given the observed rates stated above. Based on outcomes in the MAPS study, the effectiveness rate for posterior circulation subjects is expected to be very close to that of anterior circulation subjects. Therefore, the statement of power to demonstrate effectiveness for a sample size of 153 evaluable anterior circulation subjects also holds for a sample size of 153 evaluable posterior circulation subjects.

For the posterior circulation cohort, a Bayesian adaptive study design (“Goldilocks” approach) providing for interim analyses of accumulated data will be used to select the final sample-size. The first interim data analysis will occur once 100 posterior circulation subjects have been enrolled. Based on enrollment rates and the frequency of disease in the posterior circulation, at the time this interim analysis is performed it is estimated that primary endpoint data will be available for approximately 39 – 63 posterior circulation subjects. If, at an interim analysis, there is at least a 95% predictive probability of observing a true rate of complete occlusion that is higher than 50%, enrollment in the posterior circulation cohort will be stopped early for success. The maximum sample-size for the posterior circulation cohort will be no more than 180 subjects.

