Analyses for both cohorts will be performed by constructing two-sided 95% confidence intervals about the estimates of the percentage of subjects with complete aneurysm occlusion and the percentage of subjects experiencing a major ipsilateral stroke or neurological death using the exact binomial (Clopper-Pearson) method. For the effectiveness endpoint of total occlusion, the lower bound of this confidence interval will be compared to 50% for both the anterior and posterior circulation cohorts. For the safety endpoint of major ipsilateral stroke and neurological death, the upper bound of the confidence interval will be compared to 20% for the anterior circulation cohort, and 25% for the posterior circulation cohort.

Success requires safety and effectiveness endpoints to be met in each cohort separately. Success in the anterior cohort occurs when the lower bound of the effectiveness endpoint is above 50% and the upper bound of the safety endpoint is below 20%. Success in the posterior cohort occurs when the lower bound of the effectiveness endpoint is above 50% and the upper bound of the safety endpoint is below 25%.

The analysis of long-term safety and effectiveness data will be descriptive only, as no formal hypotheses will be tested based on data collected during this phase of the study. Survival analysis will be used to estimate the incidence of specified safety endpoint events, as well as retreatment of the target aneurysm. Details regarding the survival analyses are summarized in **Table 7**.

**Safety and Effectiveness of the Treatment of Wide Neck, Saccular Intracranial Aneurysms with the Neuroform Atlas™ Stent System**

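### The 85% effectiveness power carried over to the posterior cohort is 81% under the planned exact test at 62%, and 75% at the 61.1% the protocol reports from its cited source; the territory carry-over is only weakly supported

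*Combined protocol and SAP*

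**What the plan says.** For the anterior cohort, Section 4.2 begins "Assuming an effectiveness primary endpoint response rate of 62"%, credited to a published meta-analysis of Neuroform stents, and concludes: "A sample size of 153 evaluable subjects provides 85% power to demonstrate the effectiveness endpoint". The plan multiplies this by about 99% for safety to reach .842.

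The posterior cohort "will also be enrolled in order to provide 153 evaluable subjects at 12 months, with an estimated 15% attrition rate". Section 4.2 then states, on the basis of MAPS, that "the effectiveness rate for posterior circulation subjects is expected to be very close to that of anterior circulation subjects", and concludes that the anterior power statement applies to 153 posterior subjects as well. The posterior part of the synopsis repeats 62%, 85% and .842.

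Four other places bear on this:

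- **Section 1.1** describes the same meta-analysis: "complete occlusion rates on final follow-up averaged 61.1% overall in 2,111 aneurysms".
- **Section 2.4.1.1** defines the endpoint as Raymond Class 1 at 12 months "in the absence of retreatment, or parent artery stenosis (>50%) at the target location". Section 4.3 scores neurological deaths before one year as Raymond 3.
- **Section 4.6** sets the analysis, "using the exact binomial (Clopper-Pearson) method", with two-sided 95% limits, and the criterion: "Success in the posterior cohort occurs when the lower bound of the effectiveness endpoint is above 50"%.
- **Section 4.5.1, Table 3** gives MAPS Class I rates of 61/164 (37.2%) anterior and 12/33 (36.4%) posterior, P = 0.93. The text before the table says these patients had coiling without a stent.

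**The concern.** Three links carry the posterior power figure, and each is looser than the text suggests.

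1. **Method.** The 85% does not come from the interval that will decide success.
2. **Rate.** The 62% is slightly above the figure the protocol reports from its own source. That figure is an occlusion rate, while the endpoint adds further ways to fail. No deduction or justification is given.
3. **Territory.** Closeness of posterior to anterior is inferred from a non-significant comparison with 33 posterior patients who did not receive a stent.

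The posterior cohort is analysed separately and is meant to support its own indication. Anyone judging whether it is large enough is given one favourable number and no view of how fast power falls as the true rate drops below 62%.

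**Working it through.** **Inputs.** n = 153 evaluable (180 × 0.85 = 153); goal 50%; two-sided 95% limits, so 2.5% in the lower tail; planning rate 62% (Section 4.2); source rate 61.1% (Section 1.1); MAPS counts from Table 3.

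**Step 1: reproduce the plan's figure.** Normal approximation, null variance under the goal:

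z = [(0.62 − 0.50)√153 − 1.96 × 0.5] / √(0.62 × 0.38) = (1.484 − 0.980) / 0.485 = 1.039, and Φ(1.039) = 0.851.

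This matches 85%, so there is no slip in the arithmetic. The method differs from the planned analysis.

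**Step 2: decision rule under the planned analysis.** The Clopper-Pearson lower limit is 49.9% for 89/153 and 50.6% for 90/153. Success therefore needs 90 or more (58.8%). The probability of this at a true rate of exactly 50% is 1.8%.

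**Step 3: exact power**, P(X ≥ 90 | n = 153, p):

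| True composite rate | Exact power | Origin of the rate |
|---|---|---|
| 62% | 81.4% | Section 4.2 |
| 61.1% | 74.7% | Section 1.1, same source |
| 64% | 92.1% | assumed |
| 60% | 65.0% | assumed |
| 58% | 45.2% | assumed |
| 56% | 26.8% | assumed |

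The stated 85% would need a true rate of about 62.6%.

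**Step 4: combined probability.** The plan multiplies the two powers. Exact safety power is 98.9% for the anterior cohort (8% assumed, at most 20/153 events) and 98.5% for the posterior cohort (12% assumed, at most 27/153). On the plan's own product convention:

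- At 62%: 0.814 × 0.989 = 0.81 anterior; 0.814 × 0.985 = 0.80 posterior.
- At 61.1%: 0.747 × 0.989 = 0.74 anterior; 0.747 × 0.985 = 0.74 posterior.

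The plan states .842 for each.

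**Step 5: what MAPS says about territory.** 12/33 − 61/164 = 36.4% − 37.2% = −0.8 points. The Wilson limits are 22.2–53.4% for 12/33 and 30.2–44.8% for 61/164. Newcombe's interval for the difference follows:

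- Lower: −0.8 − √[(36.4 − 22.2)² + (44.8 − 37.2)²] ≈ −17 points.
- Upper: −0.8 + √[(53.4 − 36.4)² + (37.2 − 30.2)²] ≈ +18 points.

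The exact interval for 12/33 alone is 20.4–54.9%. Taking the observed difference at face value, 62% − 0.8 points gives exact power of 75.2%.

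**Step 6: direction of the endpoint mismatch.** Let O be complete occlusion and C the composite. C requires O and, in addition, no retreatment and no significant stenosis. Within the same population P(C) ≤ P(O). The documents do not say how much lower P(C) is.

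**The case against.** The 85% is a legitimate approximation and the synopsis makes it conditional on 62%. Success is still judged by the exact limit, so nothing in the test is wrong. At 62% the method alone costs under 4 points. All of that stands, and it limits the point to how power is stated and justified.

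A reader might go further in four ways that the documents do not support.

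- **That posterior power is really 27–65%.** Those are correct exact powers for true rates of 56–60%, but no document gives such a rate for this endpoint. They belong in a sensitivity table, not a conclusion.
- **That the Table 4 figures of 4% (3/69) and 14% (12/85) for stent-assisted wide-neck aneurysms can be deducted from 62%.** That column combines recanalization with retreatment. A recanalized aneurysm would generally already fail Raymond Class 1, and Appendix B defines retreatment by recanalization or in-stent stenosis. Deducting risks double counting.
- **That 23% (26/112) in the all-posterior Table 4 row against the 49% pooled rate shows a posterior deficit.** The first is all coiling; the second mixes coiling, balloon-assisted and stent-assisted treatment. Other wholly or mainly coiled wide-neck rows run from 20% to 51%, so the contrast does not isolate territory.
- **That the carry-over has no support.** The MAPS point estimates are close, and the row counts re-intervention to some degree. The support is imprecise and comes from a different treatment, but it exists.

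The true rate could also exceed 62%. Exclusion criterion 3 removes aneurysms needing a deliberate neck remnant, Section 1.2 suggests the newer design may improve outcomes, and the two stent-assisted wide-neck rows in Table 4 span 46% (32/70) to 75% (52/69). A fair table must run both ways.

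**Conclusion.** The concern holds in a limited form. At the plan's own 62%, the planned analysis has 81.4% power, not 85%; at the 61.1% reported from the cited source it has 74.7%. On figures the documents supply, the overstatement is about 4 to 10 points. The rate is also an occlusion rate used for a stricter composite, so for the same population it is an upper limit; the size of any further loss is unknown. Equality of territories rests on 33 coil-only posterior patients, with an interval wide enough to include differences of about 17 points either way.

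These figures assume 153 evaluable subjects, a single final analysis and the exact two-sided 95% limits. They are not the operating characteristics of the posterior cohort, whose final size is chosen by an adaptive design with interim analyses from 100 enrolled. The endpoint, success criterion and sample size are not in question here.

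**What to change.** In Section 4.2 and the synopsis:

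1. Replace 85% with exact-test power: 81% at 62% and 75% at 61.1%. Recalculate .842 to match (0.80 posterior and 0.81 anterior at 62%; 0.74 for both at 61.1%).
2. In Section 4.2, remove the sentence that transfers the anterior power to the posterior cohort. State instead that MAPS gave 12/33 against 61/164, a difference of −0.8 points (95% interval about −17 to +18), after coiling alone. The synopsis has no such sentence; only its figures need changing.
3. Add a short table of exact power by assumed composite rate: 27% at 56%, 45% at 58%, 65% at 60%, 81% at 62%, 92% at 64%. Label the rates as assumptions and the powers as fixed n = 153, not the operating characteristics of the adaptive posterior design.
4. Reconcile 62% with 61.1%, and say that the source rate is complete occlusion while the endpoint is a composite. Apply this and item 1 to the anterior cohort too.

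The cost is a paragraph, a five-row table and a less favourable stated power. Sample size, endpoint, test and conduct do not change.

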# **Safety and Effectiveness of the Treatment of Wide Neck, Saccular Intracranial Aneurysms with the Neuroform Atlas™ Stent System**

## **Short Study Name: ATLAS**

	
rate is greater than 50%. Assuming a safety primary endpoint rate in the posterior circulation of 12%, the expected upper bound of the exact binomial two-sided 95% confidence interval around the success rate is less than 25%.
 
A sample size of 153 evaluable subjects provides 85% power to demonstrate the effectiveness endpoint, and a power of approximately 99% to successfully demonstrate the safety endpoint given the observed rates stated above. The combined probability of the two endpoints is <math>(.85) \times (.99) = .842</math>.
 
For the posterior circulation cohort, a Bayesian adaptive study design (“Goldilocks” approach) providing for interim analyses of accumulated data will be used to select the final sample-size. The first interim data analysis will occur once 100 posterior circulation subjects have been enrolled. Based on enrollment rates and the frequency of disease in the posterior circulation, at the time this interim analysis is performed it is estimated that primary endpoint data will be available for approximately 39 – 63 posterior circulation subjects. If, at an interim analysis, there is at least a 95% predictive probability of observing a true rate of complete occlusion that is higher than 50%, enrollment in the posterior circulation cohort will be stopped early for success. The maximum sample-size for the posterior circulation cohort will be no more than 180 subjects.

Planned Number of Sites:	Up to 40 sites will participate in the clinical study.
Randomization:	This study is a non-randomized, open label, single-arm study.

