# **Safety and Effectiveness of the Treatment of Wide Neck, Saccular Intracranial Aneurysms with the Neuroform Atlas™ Stent System**

## **Short Study Name: ATLAS**

### **2.2.2 Subject Population**

Detailed subject enrollment criteria are provided in **Section 2.6, Study Population and Source of Subjects**. Up to a total of 360 subjects with wide neck, intracranial, saccular aneurysms will be enrolled as follows:

- Anterior Circulation (AC) Cohort:

Up to 180 subjects with intracranial aneurysms in the anterior circulation (excluding the petrous ICA to superior hypophyseal ICA region) may be enrolled in order to provide 153 evaluable subjects at 12 months, with an estimated 15% attrition rate. These data will be used to support a safety and effectiveness analysis for an indication for use of the Neuroform Atlas™ Stent System in the anterior circulation.

- Posterior Circulation (PC) Cohort:

Up to 180 subjects with intracranial aneurysms in the posterior circulation (including vertebral, basilar and posterior cerebral arteries) may be enrolled in order to provide 153 evaluable subjects at 12 months, with an estimated 15% attrition rate. These data will be analyzed separately from the AC Cohort data, and will be used to support an indication for use of the Neuroform Atlas™ Stent System in the posterior circulation.

For the posterior circulation cohort, a Bayesian adaptive study design (“Goldilocks” approach) providing for interim analyses of accumulated data will be used to select the final sample-size. The first interim data analysis will occur once 100 posterior circulation subjects have been enrolled. Based on enrollment rates and the frequency of disease in the posterior circulation, at the time this interim analysis is performed it is estimated that primary endpoint data will be available for approximately 39 – 63 posterior circulation subjects. If, at an interim analysis, there is at least a 95% predictive probability of observing a true rate of complete occlusion that is higher than 50%, enrollment in the posterior circulation cohort will be stopped early for success. The maximum sample-size for the posterior circulation cohort will be no more than 180 subjects.

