## **Safety and Effectiveness of the Treatment of Wide Neck, Saccular Intracranial Aneurysms with the Neuroform Atlas™ Stent System**

### **Short Study Name: ATLAS**

#### **4.6 Statistical Analysis**

All analyses will be performed using SAS, version 9.4 or higher. Some interim analyses and figures may require the use of R 3.2.3 or above.

Primary analysis will initially be carried out when data from 153 evaluable subjects from the mITT group of anterior circulation subjects are available.

Due to the substantially lower incidence of aneurysms in the posterior circulation (approximately 15-20% of diagnosed cases), the subject enrollment period for the posterior circulation cohort will be much longer in duration versus that of the anterior circulation cohort. As a result, analysis of data from the posterior circulation cohort will be completed after results for the anterior circulation subjects have already been submitted for review by the FDA, and data from that analysis will be used to support an expanded indication for use of the Neuroform Atlas™ Stent System, i.e. an indication for use in the posterior circulation. For the posterior circulation cohort, a Bayesian adaptive study design (“Goldilocks” approach) providing for interim analyses of accumulated data will be used to select the final sample-size. The first interim data analysis will occur once 100 posterior circulation subjects have been enrolled. Based on enrollment rates and the frequency of disease in the posterior circulation, at the time this interim analysis is performed it is estimated that primary endpoint data will be available for approximately 39 – 63 posterior circulation subjects. If, at an interim analysis, there is at least a 95% predictive probability of observing a true rate of complete occlusion that is higher than 50%, enrollment in the posterior circulation cohort will be stopped early for success. The maximum sample-size for the posterior circulation cohort will be no more than 180 subjects.

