### **10.2 Clinical Events Committee/Data Safety Monitoring Board (CEC/DSMB)**

The Clinical Events Committee/Data and Safety Monitoring Board (CEC/DSMB) is an independent group of experts that advises the study sponsor, Stryker, and the study investigators. The members of the CEC/DSMB serve in an individual capacity and provide their expertise and recommendations. The primary responsibilities of the CEC/DSMB are to:

- 1) periodically review and evaluate the accumulated study data for participant safety, study conduct and progress;
- 2) adjudicate pre-specified clinical events as they occur through the 12 month primary endpoint of the IDE study, and through the end of the PAS study;
- 3) make recommendations to the study sponsor concerning the continuation, modification, or termination of the trial. The CEC/DSMB considers study-specific data as well as relevant background knowledge about the disease, or patient population under study.

The CEC/DSMB shall be composed of at least three members (physicians from the fields of stroke neurology, interventional neurology, neuroradiology or vascular neurosurgery). In order to minimize any potential bias, the members of the CEC/DSMB will be independent and will not be directly involved with the conduct of the study or have any financial conflict.

The CEC/DSMB will review the study on a regular basis as described in the charter established prior to the commencement of the trial. A mission statement and procedures for the committee will be formalized in the charter. The CEC/DSMB will be responsible for reviewing aggregate safety data in order to ensure overall safety of study subjects during the execution of the trial. Guidelines for stopping rules for pre-specified safety endpoints will be established in the charter.

The Committee will be responsible for monitoring patient safety for the duration of patient enrollment and through the end of the PAS study follow up for all subjects. The study endpoints will be reviewed, and safety event causality will be adjudicated as related to the study device, procedure, both, other (specify). Data adjudicated by the independent CEC/DSMB will be used for final analysis.

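### The posterior cohort can stop early for success on effectiveness alone although success also needs the safety bound, and the stated 85%, 99% and .842 are fixed n = 153 figures, not the power of the adaptive design

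*Combined protocol and SAP*

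**What the plan says.** Section 4.6 (Statistical Analysis) makes the two primary endpoints jointly necessary: "Success requires safety and effectiveness endpoints to be met in each cohort separately". For this cohort the text reads "Success in the posterior cohort occurs when the lower bound of the effectiveness endpoint is above 50% and the upper bound of the safety endpoint", with 25% as the ceiling for the latter. Both limits come from two-sided 95% Clopper-Pearson intervals.

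The posterior sample size is adaptive, with a Bayesian design "providing for interim analyses of accumulated data will be used to select the final sample-size". The first look comes at 100 enrolled, when 39–63 subjects are expected to have endpoint data; the maximum is 180. The rule appears in the Synopsis and in Sections 2.2.2, 4.2 and 4.6. If "there is at least a 95% predictive probability of observing a true rate of complete occlusion that is higher than 50" percent, then "enrollment in the posterior circulation cohort will be stopped early for success". No safety quantity enters it.

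On power, Section 4.2 states: "A sample size of 153 evaluable subjects provides a power of approximately 99% to successfully demonstrate the safety endpoint". It carries the anterior cohort's effectiveness power over to 153 posterior subjects. The Synopsis gives 85% and about 99% for this cohort and adds: "The combined probability of the two endpoints is" .842. The paragraph on the adaptive design follows directly.

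Section 10.2 says of safety monitoring: "Guidelines for stopping rules for pre-specified safety endpoints will be established in the charter".

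**The concern.** A stop for success should mean that the trial is likely to succeed. Here it is triggered by one of two required criteria, and it can fix the sample at a size at which the other is missed more often than the plan tells its reader.

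Two further gaps make the consequence hard to see. The rule's wording does not say what is being predicted: it could be the final exact-interval result, or simply the posterior probability that the true rate exceeds 50%. And the only powers shown assume that all 153 evaluable subjects are reached, so they do not describe a design that may stop near 85. At stake is the chance of supporting the posterior indication, and whether that chance is reported correctly.

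**Working it through.** **Inputs from the documents.** Effectiveness 62% against 50%; posterior safety events 12% against 25%; two-sided 95% Clopper-Pearson limits; 180 enrolled, 15% attrition, 180 × 0.85 = 153 evaluable; first look at 100 enrolled with 39–63 completers. Complete occlusion in the rule is read as the composite endpoint, as Sections 1.6 and 2.3.1 define it.

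**1. Reproducing the stated power (fixed n = 153, normal approximation, null variance).**
- Effectiveness: z = [0.12 − 1.96·√(0.5·0.5/153)] / √(0.62·0.38/153) = (0.12 − 0.0792)/0.0392 = 1.04, power 0.8506.
- Safety: z = [0.13 − 1.96·√(0.25·0.75/153)] / √(0.12·0.88/153) = (0.13 − 0.0686)/0.0263 = 2.34, power 0.9903.
- Product: 0.8506 × 0.9903 = 0.842, the plan's figure. No interim look enters it.

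**2. The planned exact method at fixed sizes.** Effectiveness power is P(X ≥ r | n, 0.62) and safety power is P(X ≤ s | n, 0.12), where r and s are the Clopper-Pearson cut-offs.

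| Evaluable n | r | s | Effectiveness | Safety | Joint |
|---|---|---|---|---|---|
| 153 | 90 | 27 | 0.814 | 0.985 | 0.802 |
| 100 (all analysed) | 61 | 16 | 0.624 | 0.913 | 0.570 |
| 85 (100 less 15%) | 53 | 13 | 0.521 | 0.864 | 0.450 |

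The effectiveness and joint columns for 85 and 100 take no account of the favourable interim result that triggers a stop. The safety column needs no such adjustment if the endpoints are independent, because the rule does not look at safety. At n = 85, safety power is 0.958 at a 10% event rate and 0.993 at 8%.

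**3. The whole adaptive design, by simulation (40,000 trials per setting).** Assumptions that are not in the documents: flat Beta(1,1) priors, independent endpoints, looks at 100 only or at 100/120/140/160, and completers at later looks rising in step with enrolment net of attrition. For m completers with x successes and n_f evaluable at the end, the predictive probability of the final effectiveness result is P(x + Y ≥ r), with Y ~ Beta-binomial(n_f − m, 1 + x, 1 + m − x). Safety is handled in the same way with its cut-off s. Ranges cover 39 and 63 completers and both look schedules.

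| Stop quantity (≥ 95%) | Safety power | Joint power | Early stops that fail safety |
|---|---|---|---|
| Predictive, final effectiveness result only | 0.94–0.97 | 0.76–0.78 | 9–14% |
| Posterior probability that the rate exceeds 50% (literal reading) | 0.90–0.93 | 0.62–0.69 | 10–14% |
| Predictive, both final criteria | 0.98–0.99 | 0.80–0.81 | about 1% or less |

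Under the first rule, 14–19% of trials stop at the first look.

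**4. Splitting the gap from .842.** Normal approximation against exact limits: 0.842 − 0.802 = 4 points. Stop rule: 0.802 − 0.78 to 0.802 − 0.76 = about 2–4 points.

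**5. Sensitivity (first rule).**
- If 25–50% of safety events also force an effectiveness failure (Section 4.3 imputes neurological death as Raymond 3), joint power is 77–79%.
- At a 10% safety rate, safety power is about 99% and joint power about 80%.
- Type I error is 0.017–0.023 for effectiveness at a true 50% and 0.019–0.020 for safety at a true 25%. Neither exceeds 0.025.

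**The case against.** The strongest reply is that the printed powers are correctly labelled: each is tied to 153 evaluable subjects, and the plan never claims 99% at 85. The 86% applies only to trials that stop at the first look, a minority. It is also the low end of a range, because Section 4.3 imputes missing endpoints and a stop at 100 might be analysed nearer to 100, giving 91%. Section 4.2 treats 12% as a ceiling, and the matching historical rate in Table 5 (11.9%, 5/42) counts strokes of any severity, whereas the trial counts only major ipsilateral stroke and neurological death. Effectiveness is the harder endpoint to meet, posterior enrolment is slow, and the final analysis still tests safety. The CEC/DSMB also reviews accumulating safety data.

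Much of this stands and limits the size. The relevant overall figure is 94–97%, not 86%; the loss is small if the true rate is nearer 10%; and the prior and later looks are assumptions. The low joint power under the literal reading is also not mainly a safety effect: 19–23% of those early stops fail effectiveness, against 10–14% that fail safety.

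The reply does not remove the point. Twelve percent is the plan's own planning rate, and 5/42 from coiling alone cannot establish a lower one. Charter guidelines protect subjects, but nothing links them to the success stop. Labelling a figure as fixed n = 153 does not supply the missing power of the design actually used.

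**Conclusion.** The concern holds and should be fixed. The early-success rule omits one of the two criteria that define success, and the posterior powers describe a fixed design analysed by a normal approximation. Under the plan's rates and the assumptions listed above, joint power is about 76–78% on the favourable reading of the rule and 62–69% on the literal one, against the stated 84.2% and an exact fixed-design value of 80.2%.

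The missing safety term itself costs about 2–4 points at a 12% event rate and almost nothing at 10%. Success still requires both limits, and type I error is not inflated under the predictive reading. The harm is therefore lower and unreported power for the posterior indication, not a route to approving an unsafe device. Confidence is high on the text and the exact fixed-sample figures. The simulated figures should be used only as ranges.

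**What to change.** - Define the stop quantity as at least 95% predictive probability that both final Clopper-Pearson criteria (composite effectiveness lower limit above 50%, safety upper limit below 25%) will be met in the subjects already enrolled, once they are followed to 12 months. This also settles the ambiguous wording.
- State the prior, the look schedule and how subjects without 12-month data enter the prediction.
- Replace the posterior 85%, 99% and .842 with simulated power, type I error and expected sample size of the adaptive design under the exact method. Joint power with the two-criterion rule is about 80%.

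The cost is protocol and SAP wording plus a short simulation; the maximum stays at 180. Early stopping becomes rarer: 25–46% of trials instead of 43–57% with four assumed looks, and 2–9% instead of 14–19% with one. The mean evaluable sample rises by about 6–11 subjects. If the sponsor prefers to keep stopping on effectiveness alone because enrolment is slow, the plan should say so and report the resulting joint power.
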